7.6. Other Safety Measures

A data listing will be provided for participants experiencing pregnancy during the study.

7.7. Changes from Protocol-Specified Safety Analyses

No change from protocol-specified safety analyses is planned.

8. PHARMACOKINETIC EVALUATION/ANALYSIS

8.1. Pharmacokinetic (PK) Sampling and PK Concentration

PK concentration data from serum PK samples of GS-5423 and GS-2872, as well as plasma PK samples of LEN (see Section 1.2.5.3) will be listed and summarized using the PK analysis sets. PK concentration data from PK substudy participants will be analyzed separately.

8.2. Pharmacokinetic Parameters

PK parameters will be estimated using Phoenix WinNonlin® software using standard noncompartmental methods. The linear up/log down rule will be used in conjunction with the appropriate noncompartmental model, with input values for dose level, dosing time, PK concentration, and corresponding real-time values, based on drug dosing times whenever possible.

All predose sample times before time-zero will be converted to zero for the calculation of PK parameters.

For area under the curve (AUC), samples below the limit of quantitation (BLQ) of the bioanalytical assays occurring prior to the achievement of the first quantifiable concentration will be assigned a concentration value of zero to prevent overestimation of the initial AUC. Samples that are BLQ at all other time points will be treated as missing data in WinNonlin. The nominal time point for a key event (eg, urine collection) or dosing interval (τ) may be used to permit direct calculation of AUC over specific time intervals. The appropriateness of this approach will be assessed by the PK scientist on a profile-by-profile basis.

Pharmacokinetic parameters such as AUC_{inf} , λ_z and $t_{1/2}$ are dependent on an accurate estimation of the terminal elimination phase of drug. The appropriateness of calculating these parameters will be evaluated upon inspection of PK data on a profile-by-profile basis by the PK scientist.

The analytes and parameters presented in Table 8-1 will be used to evaluate the PK objectives of the study.

Table 8-1. Pharmacokinetic Parameters for Each Analyte

Analysis Set	Analyte	Sample Matrix	Parameters
LEN PK Substudy Analysis Set	LEN	Plasma	AUC_{0-26wk} , AUC_{last} , C_{26wk} , C_{max} , $C_{max\ day1}$, $t_{1/2}$, T_{last} , T_{max} , $T_{max\ day1}$
LEN PK Analysis Set	LEN	Plasma	C_{26wk} , $t_{1/2}$, T_{last}
GS-5423 PK Analysis Set	GS-5423	Serum	AUC_{0-26wk} , AUC_{last} , AUC_{inf} , $\%AUC_{exp}$, C_{26wk} , C_{max} , $t_{1/2}$, T_{max} , T_{last} , CL , V_{ss}
GS-2872 PK Analysis Set	GS-2872	Serum	AUC_{0-26wk} , AUC_{last} , AUC_{inf} , $\%AUC_{exp}$, C_{26wk} , C_{max} , $t_{1/2}$, T_{last} , T_{max} , CL , V_{ss}

8.3. Statistical Analysis Methods

8.3.1. Statistical Analysis of PK Concentration

Individual participant concentration data of LEN, GS-5423, and GS-2872 for participants in the PK analysis set will be listed and summarized using descriptive statistics by treatment group for the primary cohort, the pilot cohort, and for pooled cohorts. In addition, for LEN and GS-5423, individual participant concentration data for participants in the PK analysis set will be summarized for combined treatment groups (total) for the primary cohort, the pilot cohort, and for pooled cohorts. For the LEN PK substudy, individual participant concentration data for PK sample timepoints from Day 1 to Day 8 will be listed and summarized overall (i.e., one summary). Summary statistics (numbers of participants, mean, SD, coefficient of variation [%CV], median, minimum, maximum, Q1, and Q3) will be presented for individual participant concentration data by time point.

Individual concentration data listings and summaries will include all participants with concentration data. If a participant had quantifiable pre-dose, BLQ at end of infusion, or received incorrect dose, the related PK concentration(s) will be captured in the table but will be excluded from the summary statistics, with reasons for exclusion identified. The sample size for each time point will be based on the number of participants with nonmissing concentration data at that time point. For summary statistics, BLQ values will be treated as zero at predose and postdose time points. The number and percentage of participants with concentration BLQ, as well as an indicator if more than one-third of the participants are BLQ, will be presented for each time point. The method to handle BLQ values for PK summaries are described in Section 3.7.2. Concentration values will be presented as received from the bioanalytical lab and summary statistics will be presented to three significant digits.

Participants with viral breakthrough (i.e., HIV-1 RNA \geq 50 copies/mL at Week 26 visit as defined by the FDA-defined snapshot algorithm) will be flagged in the listings.

8.3.1.1. PK Concentration Data Based on LEN PK Substudy Analysis Set

For analyses based on the LEN PK Substudy Analysis set, PK concentration will be summarized overall (i.e., one summary).

The following tables will be provided for LEN using the LEN PK Substudy Analysis Set:

- Individual participant concentration data and summary statistics

The following figures will be provided for LEN using the LEN PK Substudy Analysis Set:

- Mean (\pm SD) concentration data versus time (on linear and semilogarithmic scales). If more than one-third of the values at a timepoint are BLQ then the mean and SD will not be presented at that timepoint and remaining points connected. If lower error bar (mean-SD) is < 0 at a timepoint then it will not be presented at that timepoint.
- Median (Q1, Q3) concentration data versus time (on linear and semilogarithmic scales). If more than one-half of the values at a timepoint are BLQ then the median and quartile values will not be presented at that timepoint and remaining points connected. If lower error bar (Q1) is BLQ at a timepoint then it will be presented as LLOQ at that timepoint.

8.3.1.2. PK Concentration Data Based on PK Analysis Sets

For analyses based on PK Analysis Sets, PK concentration for all analytes will be summarized for the primary cohort, the pilot cohort, and for pooled cohorts.

The following tables will be provided for each analyte (LEN, GS-5423, and GS-2872) using the associated PK Analysis Set:

- Individual participant concentration data and summary statistics

The following figures will be provided for each analyte (LEN, GS-5423, and GS-2872) using the associate PK Analysis Set:

- Mean (\pm SD) concentration data versus time (on linear and semilogarithmic scales). If more than one-third of the values at a timepoint are BLQ then the mean and SD will not be presented at that timepoint and remaining points connected. If lower error bar (mean-SD) is < 0 at a timepoint then it will not be presented at that timepoint.
- Median (Q1, Q3) concentration data versus time (on linear and semilogarithmic scales). If more than one-half of the values at a timepoint are BLQ then the median and quartile values will not be presented at that timepoint and remaining points connected. If lower error bar (Q1) is BLQ at a timepoint then it will be presented as LLOQ at that timepoint.
- Individual participant concentration data versus time (on linear and semilogarithmic scales). Values of BLQ will be displayed as 0 on the linear scale and missing on the semi-logarithmic scale.

In addition, the following listings will be provided for all analytes:

- Plasma PK sampling details for LEN by participant, including procedures, differences in scheduled and actual draw times, and sample age.
- Serum PK sampling details for GS-5423 and GS-2872 by participant, including procedures, differences in scheduled and actual draw times, and sample age.

8.3.2. Statistical Analysis of PK Parameters

Individual estimates of pharmacokinetic parameters of LEN, GS-5423, and GS-2872 will be listed and summarized using descriptive statistics (eg, sample size, arithmetic mean, coefficient of variation %, SD, 95% CI for the arithmetic mean, geometric mean, %CV, median, minimum, maximum, Q1, Q3, sample size of natural log-scale [LN], geometric mean, Geometric Coefficient of Variation [%GVC], 95% Confidence Interval for Geometric Mean [GCI], mean of LN, SD of LN). PK parameters for LEN, GS-5423 and GS-2872 will be summarized as described in Section 3.2.3.

PK parameters listed in Table 8-1 will be included in the following tables.

- Individual estimates and summary statistics of plasma LEN PK parameters using the LEN PK Substudy Analysis Set
- Individual estimates and summary statistics of plasma LEN PK parameters using the LEN PK Analysis Set
- Individual estimates and summary statistics of serum GS-5423 PK parameters using the GS-5423 PK Analysis Set
- Individual estimates and summary statistics of serum GS-2872 PK parameters using the GS-2872 PK Analysis Set.

PK parameters could be unestimatable due to insufficient concentration data or may be estimated but marked for exclusion due to reasons such as the participant received an incorrect dose. In such cases, the PK parameters will be included in the listing (as not reported [NR] or the estimate values) but will be excluded from the summary statistics, with reasons for exclusion identified.

In addition, determination of half-life and corresponding correlation coefficient will be provided in the following listings:

- Individual data on determination of LEN plasma half-life and corresponding correlation coefficient using the LEN PK Analysis Set
- Individual data on determination of GS-5423 serum half-life and corresponding correlation coefficient using the GS-5423 PK Analysis Set
- Individual data on determination of GS-2872 serum half-life and corresponding correlation coefficient using the GS-2872 PK Analysis Set.

9. IMMUNOGENICITY ANALYSIS

Immunogenicity to GS-5423 and GS-2872 will be evaluated based upon the incidence of anti-GS-5423 antibody, anti-GS-2872 antibody, as well as both anti-GS-5423 and anti-GS-2872 antibody formation, respectively.

9.1. Definitions

Participants Evaluable for ADA Prevalence includes all participants who have at least one reportable ADA result at baseline or post-baseline.

Participants Evaluable for ADA Incidence includes all participants who have at least one reportable ADA result at post-baseline.

ADA Prevalence refer to the proportion of participants who have at least one positive ADA sample (baseline or post-baseline) among all participants evaluable for ADA prevalence.

ADA Incidence refer to the proportion of participants who have Treatment-Emergent ADA among all participants evaluable for ADA incidence.

Treatment-Emergent ADA: includes either Treatment-Boosted or Treatment-Induced ADAs, with details been presented in the follows:

- **Treatment-Boosted ADA** is defined as positive baseline ADA sample and at least one positive post-baseline ADA sample and the (max titer of the post-baseline ADA / titer of baseline ADA) ≥ 4 . If baseline titer < 10 (10 is the minimum reportable titer value), it will be considered boosted if max titer of the post-baseline ≥ 10 . The proportion of participants who have Treatment-Boosted ADA is calculated based on the total number of participants evaluable for ADA incidence as the denominator.
- **Treatment-Induced ADA** is defined as negative or missing baseline ADA sample and at least one positive post-baseline ADA sample. The proportion of participants who have Treatment-Induced ADA is calculated based on the total number of participants evaluable for ADA incidence as the denominator.

Persistent ADA is defined as (a) Treatment-Induced ADA detected at two or more sampling time points during the study, where the first and last ADA-positive sample (irrespective of any negative samples in between) are separated by a period of 16 weeks or longer; or (b) Treatment-Induced ADA detected at the last sampling time point of the study. The proportion of participants who have persistent ADA is based on the total number of participants evaluable for ADA incidence as the denominator.

Transient ADA is defined as Treatment-Induced ADA that does not meet the definition of persistent ADA. The proportion of participants who have transient ADA is based on the total number of participants evaluable for ADA incidence as the denominator.

Participant-level ADA status is defined as (a) “ADA+” if the participant has Treatment-Emergent ADA; (b) “ADA-” if the participant is evaluable for ADA incidence and does not have Treatment-Emergent ADA; and (c) missing if the participant is not evaluable for ADA incidence.

Time to ADA onset is defined as:

- the number of days after first dose to the day when the first positive ADA result was detected for participants with Treatment-Induced ADA
- the number of days after first dose to the day when the first boosted post-baseline positive ADA result was detected for participants with Treatment-Boosted ADA.

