5.3. Dosage and Administration of GS-5423, GS-2872, and Lenacapavir

On Day 1, all participants will receive the following study regimen:

- Oral LEN 600 mg will be administered orally (PO) with approximately 240 mL water, without regard to food.
- LEN 927 mg SC will be administered within 30 minutes after oral LEN for loading, as 2 SC injections at separate injection sites in the abdomen, within 15 minutes.
- GS-5423 30 mg/kg IV infusion will be administered immediately following (up to 1 hour after) the last SC LEN injection.
- GS-2872 10 mg/kg or 30 mg/kg (depending upon treatment group assignment) IV infusion will be administered at least 15 minutes following, and up to 1 hour after, the completion of GS-5423 IV infusion per [Table 5-1](#).

On Day 1, all study drugs should be administered on the same day (ie, no visit window is permitted for Day 1 study drug administration).

On Day 2, all participants will self-administer oral LEN for loading 600 mg with approximately 240 mL water, without regard to food, at approximately the same time as the oral LEN dose for loading on Day 1.

Dose and administration of LEN, GS-5423, and GS-2872 for Treatment Groups 1 and 2 are described below.

Table 5-1. Treatment Table

Study Day	Treatment Group 1	Treatment Group 2
Day 1	LEN 600 mg (two 300 mg tablets, PO) LEN 927 mg (two 1.5 mL injections, SC) GS-5423 30 mg/kg (IV infusion) GS-2872 10 mg/kg (IV infusion)	LEN 600 mg (two 300 mg tablets, PO) LEN 927 mg (two 1.5 mL injections, SC) GS-5423 30 mg/kg (IV infusion) GS-2872 30 mg/kg (IV infusion)
Day 2	LEN 600 mg (two 300 mg tablets, PO)	LEN 600 mg (two 300 mg tablets, PO)

IV = intravenous; LEN = lenacapavir; PO = per oral; SC = subcutaneous

Supportive medications, including but not limited to diphenhydramine, acetaminophen, and steroids, will be available in the clinic settings during the IV infusions.

Study drug infusion will be temporarily stopped if an infusion-related adverse reaction occurs. Symptom severity will be evaluated, and supportive medications provided as clinically indicated. Study drug infusion may be slowed and resumed after symptoms have resolved if approved by the investigator. If the symptoms, in the judgment of the investigator, compromise the ability to continue study-specific procedures and are considered to not be in the participant's best interests, or recurrent symptoms prevent completion of infusion, the infusion will be permanently discontinued.

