3.1.6. Pharmacokinetic (PK) Analysis Sets

The PK Analysis Sets include the follows:

- LEN PK Analysis Set includes all randomized participants who have received at least 1 dose of study drug, and have at least 1 nonmissing LEN concentration value reported by the PK laboratory test.
- GS-5423 PK Analysis Set includes all randomized participants who have received at least 1 dose of study drug, and have at least 1 nonmissing GS-5423 concentration value reported by the PK laboratory test.
- GS-2872 PK Analysis Set includes all randomized participants who have received at least 1 dose of study drug, and have at least 1 nonmissing GS-2872 concentration value reported by the PK laboratory test.

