3.1.7. Immunogenicity Analysis Sets

The Immunogenicity analysis sets include the follows:

- Anti-GS-5423 Immunogenicity Analysis Set will include all randomized participants who have received at least 1 dose of study drug and have had at least 1 nonmissing value for anti-GS-5423 evaluation.
- Anti-GS-2872 Immunogenicity Analysis Set will include all randomized participants who have received at least 1 dose of study drug and have had at least 1 nonmissing value for anti-GS-5423 evaluation.
- Anti-GS-5423 and Anti-GS-2872 Immunogenicity Analysis Set will include all randomized participants who have received at least 1 dose of study drug and have had at least 1 nonmissing value for both anti-GS-5423 and anti-GS-2872 evaluation.

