3.8.1. Definition of Key Dates and Study Day

Study Day 1 is defined as the day when the first dose of any study drug was taken, as recorded on the Study Drug Administration eCRF (ie, oral LEN, SC LEN or infusion drugs [GS-5423, GS-2872]).

Last Dose Date is defined as the latest dose date of any study drug as recorded on the Study Drug Administration eCRF (ie, oral LEN, SC LEN or infusion drugs (GS-5423, GS-2872) for participants who prematurely discontinued study drug or completed study drug according to Study Drug Completion eCRF.

Study Days are calculated relative to Study Day 1 of study drug and derived as follows:

- For postdose study days: Assessment Date – First Dose Date + 1
- For days prior to the first dose: Assessment Date – First Dose Date

Baseline Value is defined as the last value obtained on or prior to the first dose of study drug.

Last Study Date is the latest clinic visit dates, and/or the laboratory visit dates, whichever is latest, including the any follow-up visit dates, for participants who prematurely discontinued study or completed study according to the Study Completion eCRF.

Last Exposure Date is defined as follows for participants who prematurely discontinued study or complete study according to Study Completion eCRF (i.e. participant answered “No” or “Yes” for “Did the participant complete the protocol-planned duration of the study” on Study Completion form):

- For participants who receive any injection or infusion, last exposure date is defined as last study date.
- For participants who do not receive any injection or infusion (i.e. for those who only receive oral LEN), last exposure date is defined as the earliest of the last dose date plus 60 days and the last study date.

The last exposure date is defined considering the prolonged exposure of LEN, GS-5423, and GS-2872 after the last dose date of LEN, GS-5423, and GS-2872 through the end of study.

Last Exposure Date of LA Regimen is defined as follows for participants who prematurely discontinued study drug or complete study drug according to Study Drug Completion eCRF (i.e. participant answered “No” or “Yes” for “Did participant complete study drug dosing as specified per protocol” on Study Drug Completion form):

- the earliest date of last study day or ART restart day for participants who prematurely discontinued study or complete study, or

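### ADA incidence for each antibody can count participants who never received that antibody, because the analysis sets and the denominator ask only for a dose of any study drug

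*SAP*

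**What the plan says.** SAP 3.1.7 opens each antibody's set the same way: "Anti-GS-5423 Immunogenicity Analysis Set will include all randomized participants who have received at least 1 dose of study drug" and "Anti-GS-2872 Immunogenicity Analysis Set will include all randomized participants who have received at least 1 dose of study drug". Each set then asks for at least one nonmissing immunogenicity value, and the combined set asks for a value on both assays. The immunogenicity set in Protocol 8.3.1.5 uses the same dose condition.

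In SAP 3.8.1, any study drug means the products "as recorded on the Study Drug Administration eCRF (ie, oral LEN, SC LEN or infusion drugs [GS-5423, GS-2872", so one oral lenacapavir dose meets the condition. The same section plans for people who get no antibody at all: "For participants who do not receive any injection or infusion (i.e. for those who only receive oral LEN".

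SAP 9.1 then defines the incidence denominator: "Participants Evaluable for ADA Incidence includes all participants who have at least one reportable ADA result at post-baseline". An evaluable participant without treatment-emergent ADA is labelled ADA-negative. The treatment-boosted, treatment-induced, persistent and transient proportions share this denominator.

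The PK sets in SAP 3.1.6 follow the same pattern, for example "GS-2872 PK Analysis Set includes all randomized participants who have received at least 1 dose of study drug".

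**The concern.** ADA incidence is meant to say how often people given an antibody make antibodies against it. Someone never given the antibody carries no information on that question, but the plan's wording places such a person in the denominator.

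The SAP handles exposure more carefully elsewhere. The Full Analysis Set (3.1.2) and the Safety Analysis Set for LA Regimen (3.1.4) require SC lenacapavir and both antibodies. The denominator for injection-site and infusion reactions (7.1.7.1) is limited to people who had an injection or infusion. The antibody-specific ADA sets lack any such condition, and nothing in SAP 9 supplies it.

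Immunogenicity is a named secondary objective, and the proportion ADA-positive at Week 26 is a secondary endpoint. With about 10 participants per dose group, one person moves a percentage visibly.

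**Working it through.** **Step 1. Can an unexposed participant enter the ADA set?** Yes. The dose condition is met by oral lenacapavir, and the predose serum sample on Day 1 (Protocol 6.7.1) can supply the nonmissing value.

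**Step 2. Does that make the person ADA-negative?** Not yet. SAP 9.1 requires a reportable post-baseline result, and without one the participant-level status is missing. ADA samples are scheduled at Weeks 4, 12, 26, 38 and 52, and none at early-termination or post-termination visits (Protocol Appendix 2). The person must therefore stay to Week 4 or later. Protocol 6.5 allows this: a participant who stops the regimen may keep attending visits to Week 52.

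**Step 3. Does another rule remove the person?** SAP 3.2 groups by actual treatment, but the ADA columns in SAP 3.2.3 and Appendix 6 are only the two full regimens and totals. The plan does not say where a participant given lenacapavir alone, or lenacapavir plus GS-5423, belongs, and no rule takes such a person out of the totals.

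**Step 4. Size.** The documents give no expected ADA incidence and no count of unexposed participants, so no plan figure for ADA can be reproduced. Inputs:

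- N: about 20 in the Primary Cohort, randomized 1:1, so about 10 per group (Protocol 4.1 and 5.1.1)
- u: unexposed but evaluable participants; not given, assumed 1 or 2
- x: exposed participants with treatment-emergent ADA; assumed 0 to 4

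If the u unexposed are all negative:

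- reported incidence = x/N
- exposed-only incidence = x/(N - u)
- reported = exposed-only × (1 - u/N)

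| N | u | x | Reported | Exposed only |
|---|---|---|---|---|
| 10 | 1 | 1 | 1/10 = 10.0% | 1/9 = 11.1% |
| 10 | 1 | 2 | 2/10 = 20.0% | 2/9 = 22.2% |
| 10 | 1 | 4 | 4/10 = 40.0% | 4/9 = 44.4% |
| 10 | 2 | 2 | 2/10 = 20.0% | 2/8 = 25.0% |
| 20 | 1 | 2 | 2/20 = 10.0% | 2/19 = 10.5% |

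**Step 5. No positives.** The estimate is 0% either way, but the amount of ADA that can be ruled out differs. The exact upper 95% limit for 0 of n is 1 - 0.025^(1/n). For n = 20 this gives 16.8%, which matches the zero-event column of Protocol Table 8-1. For n = 10 it gives 30.8%, and for n = 9 it gives 33.6%. SAP 9.2 plans no interval for ADA, so these limits only show how much reassurance a zero count would carry.

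**Step 6. The other direction.** If the unexposed participant tests positive after a negative or missing baseline, SAP 9.1 classes this as treatment-induced. With N = 10, u = 1 and one exposed positive, the report reads 2/10 = 20.0%, against 1/9 = 11.1% among the exposed.

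**The case against.** The best case against acting is that the situation may never arise and would be visible if it did. No document shows that any dosed participant missed an antibody. SAP 4.2.2 tabulates how many received each infusion, and SAP 9.2 lists each ADA result beside the matching PK concentration, so with about 20 people per cohort a reader could spot an undosed participant. The shift is also small against the uncertainty: the exact 95% interval is 0.3% to 44.5% for 1 of 10 and 0.3% to 48.2% for 1 of 9. The wording follows the protocol, so this is not a slip made in the SAP. All of this stands, and it limits the weight of the point. It does not correct the denominators, because a listing does not change a tabulated percentage.

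Three stronger readings are tempting, and the documents do not support them.

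- A reader might infer that PK means are biased, since a never-dosed participant's values below quantitation count as zero (one in 10 would lower a group mean by 10%). SAP 8.3.1 keeps concentrations out of the summary statistics when the end-of-infusion sample is below quantitation or the dose was incorrect, and SAP 8.3.2 does the same for unestimable or incorrect-dose parameters. These rules largely close that route. They do not expressly name a dose never given, and they leave set membership and the individual plots untouched.
- A reader might take the protocol's stopping rule as the source of unexposed participants: "or recurrent symptoms prevent completion of infusion, the infusion will be permanently discontinued". That rule stops an infusion under way. The person has had part of the dose, counts as exposed, and should stay in the set.
- It would follow from that reading that the unexposed are mainly people with infusion reactions, so that the dilution is not random. That is conjecture; the documents do not say who would miss an antibody or why.

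**Conclusion.** The definitions give a wrong result in a case that the SAP itself foresees: the participant given only oral lenacapavir in 3.8.1, and more generally the missed Day 1 or Day 2 doses for which 3.1.3 makes provision. The error is confined to the ADA tables. Each unexposed, evaluable, negative participant lowers incidence by a relative 10% in a group of 10 and 5% in a total of 20.

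The size rests on three assumptions that the documents do not settle: that at least one dosed participant missed an antibody, that this person gave a reportable ADA sample at Week 4 or later, and that the result was negative. If u = 0, nothing changes. Because the endpoint is descriptive, with no test or decision threshold, the point is minor. It is worth making because the definition is wrong as written and easy to put right.

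**What to change.** In SAP 3.1.7 and in the evaluable-for-incidence definition in 9.1, replace the any-study-drug condition with:

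- receipt of any amount of GS-5423 for the anti-GS-5423 set and its denominator
- receipt of any amount of GS-2872 for the anti-GS-2872 set and its denominator
- receipt of any amount of both for the combined set

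Requiring any amount, and not a full dose, keeps partly infused participants in. Use the same wording for the GS-5423 and GS-2872 PK sets in 3.1.6, so that set counts and individual plots agree with exposure. While 3.1.7 is open, also correct the anti-GS-2872 set, which is conditioned on a nonmissing anti-GS-5423 value.

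The cost is one phrase per definition and no new data, since receipt of each infusion is already recorded and summarized (SAP 4.2.2). The change departs from Protocol 8.3.1.5 (and 8.3.1.4.2 for PK), so it should be recorded as such; if the SAP is already final, SAP section 1 places that record in the clinical study report. A sentence giving the number dosed but not exposed to each antibody, even if zero, would show whether the change made any difference.
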